10.1 Disposition of Participants and Discontinuations

Subject disposition will be presented for the ES:

- Total number of subjects enrolled (i.e., subjects who gave informed consent),
- Number of subjects who discontinued from the study prior to treatment overall and grouped by the main reason (i.e., the Reason why the subject did not continue beyond screening, as recorded in the CRF. If the Subject did not meet all Eligibility Criteria, the failed specific inclusion or exclusion criteria will be provided in addition). Subjects not classified as screened failure but without treatment assignment by the iRT will be listed as “no treatment assigned”,
- Number of eligible subjects (i.e., subjects with treatment assignment by the iRT system),
- Overall and by Treatment Course, who received at least dose one of study medication,
- Who discontinued the study medication, grouped by main reason (according to the information on the Study Termination CRF page),
- Who completed the study (according to the information on the Study Termination CRF page).
- Number of Visits performed before and after Start of COVID-19 pandemic

Percentages will be presented with respect to the number of eligible subjects. The number of subjects in each analysis set will be provided overall, by region, by country within region, and by site.

The following subject data listings will be provided:

- Listing of discontinued subjects for the ITT,
- Listing of subjects excluded from the Analysis Sets.

The number of subjects with least one available T1 GD+ lesion count, T2 lesion count and CUA lesion count for each Study Period will be presented for the FAS together with the statistics for the length of the Study Periods, and statistics of the number of available T1 Gd+ lesion counts during the Study Periods.

10.2 Protocol Deviations

10.2.1 Important Protocol Deviations

The following summary tables and listings of major protocol deviations (see Section 8.1 for details) will be provided by Inclusion/Exclusion and other deviations for the ITT:

- Frequencies per reason of major protocol deviations (overall and based on relationship to COVID-19 pandemic),
- Listing of major protocol deviations (including information regarding relationship to COVID-19 pandemic).

11 Demographics and Other Baseline Characteristics

Unless stated otherwise, summaries will be presented on the FAS.

11.1 Medical History

The medical history will be coded using the Medical Dictionary for Regulatory Activities (MedDRA). Summary table will be presented by primary system organ class (SOC) and preferred term (PT).

11.2 Other Baseline Characteristics

11.3 Demographics

Demographic characteristics will be summarized using the following information from the Screening/Baseline Visit CRF pages.

Demographic characteristics:

- Gender:
 - Male,
 - Female,
 - Missing.
- Race:
 - White,
 - Black or African American,
 - Asian,
 - American Indian or Alaska Native,
 - Native Hawaiian or Other Pacific Islander,
 - Other,
 - Not collected at this site,
 - Missing.
- Ethnicity Hispanic or Latino:
 - Yes,
 - No,
 - Missing.
- Ethnicity Japanese:
 - Yes,
 - No,
 - Missing.

- Age (years)
- Age categories:
 - ≤ 40 years,
 - 40 years, < 65 years,
 - ≥ 65 years,
 - Missing.
- Region:
 - Eastern & Central Europe: Austria, Germany, Hungary, Poland, Czech Republic
 - Scandinavia: Finland, Sweden
 - Mediterranea: Italy, Spain
 - Western Europe: France, United Kingdom
 - Australia,
 - Canada,
 - Israel.
- Country
 - Country 1
 - ...
- Pooled Centers

The following subject data listing will be provided:

- Demographic Data (Country, Sex, Race, Age, EDSS at Baseline, Number of relapses within 12 months prior to Baseline).

MS Disease Characteristics

The duration since onset and diagnosis of MS at Baseline in months, as well as the EDSS at Baseline, will be presented. In addition, the number of subjects grouped by the major systems affected (at onset of MS) will be presented.

- Time since onset of MS (months) = (Visit start date of Baseline Visit - date of first symptom + 1) / 30.4375,
- Time since diagnosis (months) = (Visit start date of Baseline Visit - date of diagnosis + 1) / 30.4375,
- Time since first relapse (months) = (Visit start date of Baseline Visit - date of first relapse + 1) / 30.4375,

- Number of previous DMDs (i.e., number of different PTs of DMDs as entered into the “Relevant Previous Medication Form” (see Appendix 1)),
 - 0
 - 1
 - 2
 - >2
- EDSS at Baseline,
- EDSS at Baseline,
 - ≤ 3
 - > 3
 - Missing
- Number of historical relapses within 12 months prior to Baseline (i.e., number of relapses from the “MS Relapse History Baseline” eCRF page):
 - Baseline Visit Start Date \geq onset date \geq Baseline Visit Start Date - 396 Days, if the day of the onset is available,
 - Month of the Baseline Visit Start Date \geq onset month \geq month of Baseline Visit Start Date – 13 months, if only the month of onset is available.
- Number of historical relapses within 12 months prior to Baseline categorized to:
 - 0
 - 1
 - 2
 - >2
- High-relapse activity (HRA)
 - Yes
 - No

Missing days or months of the dates of first symptom, diagnosis, first relapse will be replaced by 1.

MRI Baseline Characteristics

The following selected results of the independent MRI review for the Baseline Period will be presented:

T1 Gd+ lesions:

- Mean T1 Gd+ lesion count for the Baseline Period
- Mean T1 Gd+ lesion count for the Baseline Period
 - 0
 - >0
 - Non-evaluable
 - Missing
- T1 Gd+ lesion count at the Screening Visit
- T1 Gd+ lesion count at the Screening Visit
 - 0
 - 1
 - >1
 - Non-evaluable
 - Missing
- T1 Gd+ lesion count at the Baseline Visit
- T1 Gd+ lesion count at the Baseline Visit
 - 0
 - 1
 - >1
 - Non-evaluable
 - Missing
- New T1 Gd+ lesion count at the Baseline Visit
- New T1 Gd+ lesion count at the Baseline Visit
 - 0
 - 1
 - >1
 - Non-evaluable
 - Missing

T1 Gd+ lesion volume:

- T1 Gd+ lesion volume at the Screening Visit
- T1 Gd+ lesion volume at the Baseline Visit

T1-hypointense lesions:

- T1-hypointense lesion count at the Screening Visit
- T1-hypointense lesion count at the Baseline Visit

T1-hypointense lesion volume:

- T1-hypointense lesion volume (cm³) at the Screening Visit
- T1-hypointense lesion volume (cm³) at the Baseline Visit

Total T2 lesions:

- Total T2 lesion count at the Screening Visit
- Total T2 lesion count at the Baseline Visit

Total T2 lesion volume:

- Total T2 lesion volume (cm³) at the Screening Visit
- Total T2 lesion volume (cm³) at the Baseline Visit

Active T2 lesions:

- Total active T2 lesion count during Baseline Period
- Total active T2 lesion count during Baseline Period
 - 0
 - 1
 - >1 - < 9
 - ≥9
 - Non-evaluable
 - Missing
- Standardized total active T2 lesion count during the Baseline Period
- Annualized total active T2 lesion count during the Baseline Period
- Standardized /Annualized total active T2 lesion count during the Baseline Period
 - 0
 - >0
 - Non-evaluable
 - Missing

- Standardized total active T2 lesion count (without T1 Gd+) for the Baseline Period
- Annualized total active T2 lesion count (without T1 Gd+) for the Baseline Period
- Standardized /Annualized total active T2 lesion count (without T1 Gd+) for the Baseline Period
 - 0
 - >0
 - Non-evaluable
 - Missing

CUA lesions:

- Standardized CUA lesion count for the Baseline Period
- Annualized CUA lesion count for the Baseline Period
- Standardized /Annualized CUA lesion count for the Baseline Period
 - 0
 - >0
 - Non-evaluable
 - Missing

Note: While standardized lesion count is used in the 6-month IA, the annualized lesion count is used in the final analysis.

Vital Signs

The following Baseline characteristics will be provided in summary tables:

- Height, weight, body surface area, body mass index
- Body temperature, heart rate, Systolic Blood Pressure, Diastolic Blood Pressure

The body surface area (BSA) and body mass index (BMI) will be calculated with the following equations:

- $BSA(m^2) = ([height(cm) * weight(kg)] / 3600) ^ 0.5$
- $BMI (kg/m^2) = [weight (kg) / height (cm)^2] * 10000$

12 Previous or Concomitant Medications/Procedures

Concomitant medications are medications, other than study medications, which are taken by subjects during the study.

Concomitant medications will be summarized from the “Concomitant medication” eCRF page. ATC-1st level and preferred term will be tabulated as given from the WHO-DD dictionary current version. In case multiple ATC’s are assigned to a drug, all ATC-1st level will be used for reporting. All medications entered into the “Concomitant medication” eCRF page will be assumed to be “concomitant” irrespective of the actual start and end dates. In addition, all concomitant medications as well as concomitant medications given for disease related conditions will be presented by PT and by decreasing frequency.

Relevant previous medications are medications, other than study medications, which stopped before enrolment (i.e. date of informed consent [IC]). DMDs (see Section 8.2) administered between IC and start of study medication are major PDs that will be reported as relevant previous medications as well.

Relevant previous medications will be summarized from the “Relevant previous medication details” eCRF page. ATC-1st level and preferred term will be tabulated as given from the WHO-DD dictionary current version. In case multiple ATC’s are assigned to a drug, all ATC-1st level will be used for reporting. All medications entered into the “Relevant previous medication details” eCRF page will be assumed to be “previous” irrespective of the actual start and end dates. In addition, all relevant previous medications and relevant previous medications given for disease related conditions will be presented by PT and decreasing frequency.

All relevant previous medications which are classified as DMDs will be presented by PT. DMDs which are taken within 6 months prior to start of study medication (i.e. DMD end date \geq start of study medication - 182.625) will be presented by PT. The length of the washout Period (start of study medication - DMD end date + 1) of the last DMD within 6 months prior to start of study medication will be summarized. The last DMD will be defined as the DMD with the latest stop date. If the DMD end date is partially missing, the day will be imputed by the 15th of the month but the date will be truncated to IC date -1 if the imputation results in a later date. If the month is missing as well or the date is completely missing the end date will not be replaced and it assumed that the DMD stopped earlier than 6 months prior to start of study medication.

Concomitant procedures which were undertaken any time on study will be listed by subject for the SAF.

13 Treatment Compliance and Exposure

Two years of treatment are planned in this study. Subjects will take tablets in Week 1 (Treatment week 1) and Week 5 (Treatment week 2) of each year. All dosing calculations and summaries will be based on “Treatment Administration” and “Treatment Termination” eCRFs pages.

The following summary tables will be provided for the SAF:

- Duration of therapy,
- Compliance and Drug Accountability

The duration will be presented for Treatment Course 1 Treatment Period, Treatment Course 2 Treatment Period and the Treatment Period in days.

- Duration (days)= (date of last tablet in Period – date of first tablet in Period + 1)

Counts of tablets and compliance will be calculated first for each treatment week:

- Compliance (%) = $100 * \text{number of tablets taken during the treatment week} / \text{number of planned tablets for the treatment week}$

If a subject discontinued the treatment before the start of the respective treatment week, compliance will not be derived for this week. If the subject did not take any tablet during the respective treatment week, but had not discontinued the treatment before, compliance will be 0. If the subject was treated during the respective treatment week, but the number of tablets is unknown, compliance will be missing.

Compliance for each year (course) and total will be calculated for all subjects that started the respective treatment period (i.e. taken at least one tablet) as an average of available records obtained for the corresponding treatment weeks. That means, treatment weeks after the subject’s treatment discontinuation are not included in the derivation, records of 0 compliance for the corresponding treatment weeks are included in the derivation as such, and missing records result in missing compliance for the respective treatment period.

In addition, compliance will be categorized as follows:

- < 60%
- [60%-80%[
- [80%-90%[
- [90%-110%]
- >110%

The number of planned tablets is based on the weight at the beginning of each treatment course (Table 2).

Table 2: Dose of Mavenclad® per treatment week by subject weight in each treatment year

Weight range	Dose in mg (number tablets) per treatment week	
	Treatment week 1	Treatment week 5
40 to <50	40 mg (4 tablets)	40 mg (4 tablets)
50 to <60	50 mg (5 tablets)	50 mg (5 tablets)
60 to <70	60 mg (6 tablets)	60 mg (6 tablets)
70 to <80	70 mg (7 tablets)	70 mg (7 tablets)
80 to <90	80 mg (8 tablets)	70 mg (7 tablets)
90 to <100	90 mg (9 tablets)	80 mg (8 tablets)
100 to <110	100 mg (10 tablets)	90 mg (9 tablets)
110 and above	100 mg (10 tablets)	100 mg (10 tablets)

The number of subjects with the same planned dosing schema in both Treatments Courses and a different planned dosing schema (i.e. subjects exchanged weight range as defined in the table above) in Treatment Course 2 will be presented for all subjects, who have started Treatment Course 2 (i.e. taken at least one tablet in Treatment Course 2).

The time difference between the start of the Treatment Course 1 Treatment Period and the start of the Treatment Course 2 Treatment Period will be calculated as follows:

- Relative Start of Treatment Course 2 (days) = Start of Treatment Course 2 - Start of Treatment Course 1 + 1.

The Relative Start of Treatment Course 2 will be presented together with the number of subjects in the following groups for the SAF:

- Treatment Course 2 not started,
 - and discontinued before the Month 12 Visit,
 - and discontinued at or after Month 12 Visit
 - Lymphocyte count < 800 cells/mm³ at Month 12 Visit,
 - Reason potentially related to COVID-19
- Treatment Course 2 started,
 - and not delayed (see Section 9 for definition),
 - and delayed,
 - and any Lymphocyte count < 800 cells/mm³ at or after Month 12 Visit and before start of Treatment Course 2.
- Before or at / after Start of COVID-19 pandemic

The cumulative dose is defined as the sum of the number of tablets taken 10 mg divided by the weight for treatment year:

Cumulative dose = number of tablets taken in Treatment Course 1 * 10mg / weight in kg at Baseline + number of tablets taken in Treatment Course 2 * 10mg / weight in kg at Month 12b Visit.

The cumulative dose will be calculated only if the weight and number of tablets are available. Otherwise it will be missing. If the Treatment Course 2 wasn't started (i.e. no tablet taken in Treatment Course 2), the cumulative dose will be calculated only for the Treatment Course 1.

A subject data listing of the treatment compliance will be provided for the SAF.

14 Efficacy Analyses

The following sections describe the planned analyses for each of efficacy endpoints.

For the detailed definition of covariates and stratification factors that are used in the statistical models see Section 9. Details about the derived MRI endpoints and general handling of MRI data is described in Section 9 (“Data Handling of MRI data”).

Descriptive summary statistics will be presented for the absolute values and the changes from Baseline as applicable by Visit [Protocol Scheduled Visits except for Baseline (defined in Section 9)], or Period, for all efficacy endpoints (and the components, where applicable) for the FAS and respective subgroups or subsets for which the variables are analyzed. Details about the presentation of continuous and categorical variables are given in Section 9.

Wherever possible, all estimated results from the statistical models will be calculated with the same observed margin which reflects the population of the whole corresponding analysis set, regardless of missing data.

14.1 Primary Endpoints: Differences in the counts of CUA MRI lesions during the first 6 months compared to Baseline

The primary endpoints for the trial are defined as the differences in counts of CUA MRI lesions during the first 6 months compared to Baseline, i.e., the following differences will be evaluated:

1. Period of Month 1 to Month 6 compared to the Baseline Period.
2. Period of Month 2 to Month 6 compared to the Baseline Period.
3. Period of Month 3 to Month 6 compared to the Baseline Period.

For the detailed definition of Periods, please see Section 9 “Data Handling of MRI data”.

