5.3.1 Inclusion Criteria

To be eligible for inclusion into this study, the subjects must fulfill all of the following criteria:

1. Subjects must voluntarily give written informed consent. Subjects must read and fully understand the Informed Consent Form (ICF) and the requirements of the trial and must be willing to comply with all trial visits and assessments
2. Male or female subjects ≥ 18 years old
3. Highly active relapsing MS as defined by:
 - One relapse in the previous year and at least 1 T1 Gd+ lesion or 9 or more T2 lesions, while on therapy with other DMDs.
 - Two or more relapses in the previous year, whether on DMD treatment or not
4. EDSS score ≤ 5.0
5. Female subjects of child-bearing potential must use highly effective methods of contraception to prevent pregnancy for 4 weeks before initiation of Mavenclad[®] and must agree to continue to practice adequate contraception for at least 6 months after the last dose (see [Appendix 12: Birth control methods which may be considered as highly effective](#)). A woman is considered of child-bearing potential (WOCBP), i.e. fertile, following menarche and until becoming post-menopausal unless permanently sterile. Women using systemically acting hormonal contraceptives should add a barrier method during Mavenclad[®] treatment and for at least 4 weeks after the last dose in each treatment year.
6. WOCBP must not be pregnant nor lactating or breast-feeding at Screening through at least 1 week after the last dose
7. Male subjects must be willing to use a condom in addition to having their female partner use another form of contraception (such as an intra-uterine device [IUD], barrier method with spermicide, or hormonal contraceptive [e.g., implant, injectable, patch or oral]) from Baseline until 6 months after the last dose of Mavenclad[®], unless their partners are infertile or surgically sterile.
8. Subjects who test positive for Varicella Zoster virus (VZV) will be included. In case of negative serology, the subject may be included after 4 to 6 weeks of receiving VZV vaccination.

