8.2 Definition of Analysis Sets and Subgroups

Enrolled Set (ES)

All subjects enrolled in the study, i.e., all subjects with a signed informed consent.

Intent-to-treat Set (ITT)

All subjects classified as eligible (i.e., medication assigned by iRT at the Baseline Visit).

Full Analysis Set (FAS)

All subjects in the ITT treated with at least one dose of study medication.

Treatment Completer Set – Year 1 (TCS-1)

All subjects from the FAS who completed the full Treatment Course of the first year (Treatment Course 1). Subjects will be classified as Treatment Completer for the first year if they have a compliance greater than or equal to 100% for Treatment Course 1.

Treatment Completer Set – Year 2 (TCS-2)

All subjects from the FAS who completed the full Treatment Course of the first and the second year. Subjects will be classified as Treatment Completer for the second year if they have a compliance greater than or equal to 100% for Treatment Course 1 and Treatment Course 2 and received the treatment without delay (see Section 9 for definition).

Safety Analysis Set (SAF)

All subjects treated with at least one dose of study medication.

Unless otherwise specified, all efficacy analyses will be performed on the FAS.

Some tertiary analyses will be repeated on the Treatment Completer Sets and the primary analysis, on the ITT (if different from FAS), to evaluate the robustness of the primary results to deviations of the planned treatment regimen. Further details are given in the respective sections. All safety analyses will be performed on the SAF.

Additional Subgroup or Subset Analysis Sets

Subgroup analyses will be performed on subgroups as defined below.

- High-relapse activity (HRA)
 - HRA: at least 2 relapses in the previous year (i.e. the number of historical relapses within 12 months prior to Baseline ≥ 2) regardless of prior use of DMDs
 - Non-HRA: otherwise

Unless otherwise indicated, all descriptive statistical analyses will be presented separately for the HRA subgroups.

- Previous treatment with Disease Modifying Drugs (DMDs):
 - DMD pre-treated: Subjects will be categorized as DMD pre-treated if they have taken DMDs any time before start of study medication. Details of the definition of DMDs are specified in Appendix 1 (Section 18.1).
 - Pre-treatment naïve: all subjects not classified as DMD pre-treated.

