- End = Start of study medication at or after the Month 12 Visit - 1 day, or if the subject did not receive Treatment Course 2: Start of study medication of Treatment Course 1 + 457 days (which is obtained by 360 (12 months) + 90 (3 months) + 7 (Visit window)) or date of discontinuation, if earlier.

Course 2 Treatment Period:

- Start = Start of study medication at or after the Month 12 Visit,
- End = End of Treatment Period.

Definition of Delayed Treatment Course 2

The Treatment Course 2 will be defined as delayed, if the start of study medication is delayed by more than 3 months (= 90 days) or did not start at all i.e.:

- Start of Study medication of Treatment Course 2 > Start of Study Medication of Treatment Course 1 + 457 days (which is obtained by 360 (12 months) + 90 (3 months) + 7 (Visit window)), or
- Treatment Course 2 never started (i.e., no study medication taken at or after the Month 12 Visit).

Data handling in case of a Delayed Treatment Course 2

For subjects with a Delayed Treatment Course 2, only data observed during the Course 1 Treatment Period will be analyzed in all efficacy analyses. Efficacy data after the Course 1 Treatment Period will be counted as missing in the statistical analyses and marked in the listings. In all efficacy analyses defined by Period, the subject will be classified as if the subject discontinued at the end of the Course 1 Treatment Period. For subjects without a delay the whole Treatment Period will be analyzed.

For all other analyses (except efficacy) the data is not limited to the Course 1 Treatment Period for subjects with a Delayed Treatment Course 2.

Definition of start of COVID-19-Pandemic

The start of COVID-19 pandemic will be defined by country as the earliest date of either the date of the first death from COVID-19 occurred in each country according to the published data by European Centre for Disease Prevention and Control on 26th June 2020 (<https://www.ecdc.europa.eu/en/publications-data/download-todays-datageographic-distribution-covid-19-cases-worldwide>) or 11th March 2020 (when the WHO declared COVID-19 pandemic).

Visit timing with respect to COVID-19 pandemic

A Visit is defined to be performed after the start of COVID-19 pandemic if the Visit end date is greater than the start of COVID-19 pandemic date.

Conversion factors

The following conversion factors will be used to convert days into months or years for all observations except Visit related dates:

- 1 month = 30.4375 days,

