- 1 year = 365.25 days.

Time window

- Day 1 is the day of start of study medication, the day before is Day - 1 (no Day 0 is defined),
- Study day / Treatment day is defined relative to Day 1.

The Visit schedule is defined as follows:

- 1 month = 30 days,
- 1 year = 360 days,

relative to the start date of the Baseline Visit for Treatment Course 1 and relative to the start date of the Month 12b Visit as defined in the eCRF (see also Section 15.3) for Treatment Course 2.

In each analysis, should assessments be delayed, subjects' assessment data will be treated as though it occurred at the time point specified (i.e., out of Visit windows will be not excluded or adjusted for any analyses) and inferences will be conducted accordingly. Thus, further time windows will not be specified.

All observations from unscheduled Visits will be included only in the analyses of Visit independent summaries (e.g. counts of events, progressions or worst value during Treatment Period) unless for the unscheduled Visits prior to start of study medication and the last assessment available. In case of unscheduled Visits prior to start of study medication, these will be considered to define Baseline. In the last missing case the ET Visit will be imputed by the unscheduled Visit.

The assessments of the ET Visit will be mapped to the nearest planned post-Baseline Visit with a missing assessment before or after the ET Visit of the individual assessment for all statistical analyses and descriptive summaries. As not all assessments of the ET are performed at each Visit, the different assessments of the ET can be assigned to different Visits. If the duration (in days) between the ET Visits and two missing planned Visits are equal, then the assessment will be assigned to the later Visit.

Handling of missing data

Unless otherwise specified in respective sections, missing data will not be replaced.

The handling of missing covariate and stratification factor information is described below.

The handling of missing DMD end date is described in Section 12.

Incomplete or missing onset dates of relapses from "MS Relapse Report" will be imputed as follows:

- In cases where the onset date is partially missing but the onset month and year, or the onset year are equal to the start of study medication or the date is missing then the onset date will be replaced by the start date of study medication.

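### The High-relapse-activity subgroup is defined on relapses within 12 months before Baseline, but the count behind it reaches back 396 days, or to Baseline month minus 13

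*SAP*

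**What the plan says.** SAP 8.2 gives the subgroup definition: "HRA: at least 2 relapses in the previous year (i.e. the number of historical relapses within 12 months prior to Baseline ≥ 2", regardless of earlier disease-modifying treatment. Everyone else is non-HRA. The wording mirrors one of the two routes into the trial in Protocol 5.3.1: "Two or more relapses in the previous year, whether on DMD treatment or not".

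SAP 11.3, under MS Disease Characteristics, derives the count. The variable is labelled "Number of historical relapses within 12 months prior to Baseline" and uses relapses entered on the MS Relapse History Baseline eCRF page. The lower bound has two branches:

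- full onset date known: "Baseline Visit Start Date - 396 Days, if the day of the onset is available";
- otherwise, the Baseline month minus "13 months, if only the month of onset is available".

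Both bounds are inclusive. The conversion factors in SAP Section 9, for dates that are not Visit related, are "1 month = 30.4375 days" and "1 year = 365.25 days". Protocol 7.1.3 asks sites to record at Baseline the relapses of the last 12 months.

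HRA is the default split for descriptive statistics (SAP 8.2). It is also used in repeat analyses of the primary endpoint (14.1.2), in tertiary MRI models (14.3.1 to 14.3.3 and 14.3.7) and in the treatment-emergent adverse event tables (15.1.1).

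**The concern.** The definition and the derivation describe different windows under one label, and the SAP does not explain the extra month. Imprecise dates cannot be the stated reason for the 396-day branch, because that branch applies only when the day is known.

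Eligibility admits subjects with one relapse (with MRI criteria, on treatment) as well as subjects with two or more, so the boundary between one and two relapses runs through the enrolled population. Lengthening the window can move a subject across it in one direction only, into HRA. The same count feeds the baseline table and the demographic listing under a 12-month label.

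The two branches also disagree with each other, so HRA status can turn on how completely a date was recorded rather than on disease activity.

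**Working it through.** **1. Is 396 days equal to 12 months under any SAP convention?**

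| Reading | Days | Difference from 396 |
|---|---|---|
| 12 × 30.4375 (Section 9 conversion) | 365.25 | 30.75 |
| 12 × 30 (Section 9 Visit schedule) | 360 | 36 |
| 365.25 + 7-day Visit window | 372.25 | 23.75 |
| 13 × 30.4375 | 395.69 | 0.31 |
| 365 + 31 | 396 | 0 |

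Only a 13-month reading reproduces the figure: 396 / 30.4375 = 13.01 months. Against 365.25 days the window is longer by 30.75 days, or 30.75 / 365.25 = 8.4%. The SAP's other look-back, six months for earlier disease-modifying drugs in Section 12, is converted exactly as 6 × 30.4375 = 182.625 days, with no added month.

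**2. How far does the month-only rule reach?** Month minus 13 up to the Baseline month, inclusive, covers 14 calendar-month labels. The earliest admissible onset is the first day of month minus 13.

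- Shortest reach: Baseline 1 March 2019, earliest onset 1 February 2018: 365 + 28 = 393 days.
- Longest reach: Baseline 31 August 2020, earliest onset 1 July 2019: 366 + 61 = 427 days.

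**3. Do the branches agree?** Take Baseline 31 January 2019 and onset 15 December 2017: 365 + 47 = 412 days. With the day recorded, the relapse is excluded (412 > 396). Recorded only as December 2017, it is counted.

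**4. How many subjects could move?** The documents give no relapse rate for days 366 to 396. Assume a constant Poisson rate r per year, independent of what happened in the last 12 months. The chance of at least one relapse in the extra window is 1 − exp(−r × 30.75 / 365.25):

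| Assumed r per year | Chance |
|---|---|
| 0.25 | 2.1% |
| 0.5 | 4.1% |
| 1 | 8.1% |
| 2 | 15.5% |

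A headcount would need a second undocumented assumption, the share of subjects with exactly one relapse, so none is given.

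**5. What does the split touch?** The Wilcoxon sequence and the mixed model in SAP 14.1.1 use the whole FAS. The model adjusts for Baseline score, age, EDSS and pooled centre; HRA is not a term in it.

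**The case against.** The best defence is that the rule is deliberate and harmless. It is written out, reproducible, and both branches express a nominal 13 months. An allowance for the gap between screening and Baseline is plausible. Protocol 7.1.1 records relapses of the past 12 months at screening, inclusion criterion 3 does not tie the previous year to Baseline, and the screening and Baseline MRIs must be at least 4 weeks apart. Twelve months before a screening held 28 days earlier already reaches 365 + 28 = 393 days. A strict 365-day rule could then put subjects who qualified with two relapses at screening into non-HRA.

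Much of this stands as a possible motive, but the SAP does not state it. It also covers only the short end of the gap: with screening 3 months plus 7 days before Baseline, the same logic gives 365.25 + 91.31 + 7 = about 464 days.

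The second defence is that the eCRF page may hold only relapses that sites judged to fall within 12 months. The wider bound would then move few or no subjects. The documents do not settle this, so the size must stay open.

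A reader might infer that 8% to 16% of single-relapse subjects are in fact misplaced. That does not follow. It requires rates of 1 to 2 per year that appear nowhere in the documents, and the upper rate is high for people selected for a single relapse in a year.

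**Conclusion.** The label and the derivation contradict each other, and the text needs correcting. The window is 13 months when the day is known and up to about 427 days when only the month is known. The number of subjects affected cannot be obtained from the documents. The range of about 2% to 16% of single-relapse subjects rests on assumed rates of 0.25 to 2 per year and a constant Poisson process, and it also presumes that the eCRF page captured onsets beyond 12 months.

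The exposed results are the HRA subgroup analyses, the descriptive splits, the adverse event tables by HRA and the baseline relapse summary. A reader might go further and infer that the primary conclusion is at risk. It is not: the confirmatory test neither uses nor adjusts for HRA. Nor do the documents show that the extra month was a slip; they show only that it is unexplained. This is a small point that is cheap to repair.

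**What to change.** Choose one of two routes.

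- **Align the derivation.** Use Baseline Visit start date minus 365 days when the onset day is known, and Baseline month minus 12 when only the month is known. Month-only dates stay imprecise by up to a month: for Baseline 31 March 2020, an onset recorded as March 2019 could lie 366 + 30 = 396 days back. The SAP should say that this is accepted.
- **Keep the window and declare it.** State the 396-day / 13-month window and its reason in the HRA definition and in every table label, and repeat the HRA split with 365 days. SAP Section 7 shows that the primary analysis preceded this version of the plan, and 14.1.2 marks the HRA repeats of the primary endpoint as 6-month analyses. This route therefore avoids silently redefining a subgroup already analysed.

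Under either route, list the subjects whose HRA status depends on an onset outside 12 months, with the onset date and whether its day was known. That listing replaces the assumed rates with the actual count.

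The cost is two constants or a few lines of text, one listing and, for the second route, one extra sensitivity run. Under the first route a few subjects may change subgroup, and HRA results already produced at 6 months would have to be rerun to match.
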